7.2.	Records and data retention	17

Revision #: 1.0

Page: 4 of 20

8.	Device accountability	17
9.	Informed consent process	17
10.	Adverse events	17
10.1.	Characteristics of AEs	18
10.2.	Reporting of AEs and SAEs	19
10.3.	Anticipated device-related AEs	19
11.	Patient confidentiality & data protection	19
12.	Guidelines and applicable documents	19
13.	Reference	20

Revision #: 1.0 Page: 5 of 20

1. Synopsis

Title	A prospective, single arm, open label study of the safety and efficacy of Nerivio™ for the acute treatment of New Daily Headache Persistence (NDHP) in adolescents	
Principal Investigator	[name]	
	Director, Pediatric Headache Program	
	Associate Professor of Pediatrics and Child Neurology, George Washington	
	School of Medicine and Health Sciences	
	Children's National Hospital, Washington, DC	
Investigational	Nerivio [™] is an FDA-authorized Remote Electrical Neuromodulation (REN) device for the acute treatment of migraine with or without aura in patients	
Device	12 years old or above. The device delivers transcutaneous electrical	
	stimulation to the upper arm to induce conditioned pain modulation (CPM) that	
	activates a descending endogenous analgesic mechanism.	
Objectives	To evaluate the safety and efficacy of Nerivio™ in the acute treatment of New	
	Daily Headache Persistence (NDHP) in adolescents (12 to 17 years of age).	
Participant	Adolescents 12-17 years old meeting the International Headache Society	
Population	criteria for New Daily Persistent Headache (NDPH)	
Sample size	Up to 100 participants	
Inclusion Criteria	1. Participants age 12-17 years old at the time of informed consent, inclusive.	
	2. Participants have at least a 6-month history of headaches that meet the diagnostic criteria for New Daily Persistent Headache (NDPH)	
	3. Participants who are on stable dosing of prophylaxis agents for at least three months.	
	4. Participants have personal access to a smartphone (24/7)	
	5. Participants must be able and willing to comply with the protocol	
	6. Parents/Guardians must be able and willing to provide written informed consent	
	7. Participants must be able and willing to provide informed assent	
Exclusion Criteria	Participants with an implanted electrical and/or neurostimulator device (e.g. cardiac pacemaker, cochlear implant).	
	2. Participants with congestive heart failure (CHF), severe cardiac or	
	cerebrovascular disease.	
	3. Participants with epilepsy.4. Participants who have undergone nerve block (occipital or other) in the	
	head or neck, or treatment with onabotulinum toxin A (Botox) to the head	
	and/or neck in the prior four months.	
	5. Current participation in any other clinical interventional study	
	Participants without basic cognitive and motor skills required for operating a smartphone.	
	7. Pregnant or breastfeeding females	
	8. Participants who have previous experience with the device	
	9. Participants with arm circumference below 7.9 inches (20 cm)	
Study Design	A prospective, single arm, open label trial.	
	The study will be conducted in two phases:	

Revision #: 1.0

Page: 6 of 20

	Phase I - Run-in: Eligible participants will use a smartphone headache diary application for 28 days. Participants who report at least 22 entries (70%) AND a constant and unremitting headache will be included in the treatment phase. The C-SSRS will be administered at the screening visit and a "since last visit" form which will be administered at each subsequent in-clinic study visit to assess possible suicidal ideation and behavior. The C-SSRS will be scored by the investigator or Study Coordinator who has C-SSRS certification. The survey will be scored immediately after taken by participant. If reports of suicidal ideation with intent to act (endorse item 4 or 5), reports of actual, aborted, or interrupted suicide attempts, or reports of behavior preparatory for an attempt are identified, the investigator" will refer the subject for further examination. Phase II - Treatment phase: Participants who meet the run-in requirements will receive an active Nerivio device. Participants will be instructed to use the device within 60 minutes of awakening with a headache or upon increasing headache severityduring a period of 4 week. A treatment session is of 45 minutes The participants will use the app to record pain intensity levels at baseline and 2-hours post-treatment, and to record the presence/absence of associated	
Qualifying NDHP attack	A qualifying NDPH attack is defined as a headache that: 1. is at an intensity above their baseline pain 2. is present upon awakening	
Primary endpoint	Pain relief at 2 hours post-treatment: The proportion of participants achieving pain relief at 2 hours post-treatment in the test treatment, with no use of rescue/abortive medication (Pain relief defined as a reduction from severe to moderate, mild or none, moderate to mild or none, or mild to none)	

Revision #: 1.0

Page: 7 of 20

Within-patient consistency

The repeatability of headache reduction, as described in the primary endpoint definition, in subsequent treated attacks. Thus, this endpoint measures the % of patient responding to the primary endpoint in at least 50% of their treated attacks

Disappearance of associated symptoms at 2 hours post-treatment

Disappearance of nausea, photophobia and phonophobia at 2 hours post-treatment

Functional disability at 2 hours post-treatment

The proportion of participants achieving improvement of at least one grade in functional disability in the test treatment at 2 hours post-treatment with no use of rescue medication

Improve of quality of life

Reduction in average headache disability as measured by PedsMIDAS before and at 1 month after initiation of treatment with REN.

Revision #: 1.0 Page: 8 of 20

Exploratory endpoints	 Reduction in average headache intensity at 1 month after initiation of treatment with REN Reduction in perceived stress as it relates to headache, and adverse reactions experienced as measured by HIT-6.
Safety endpoints	 The safety of Nerivio The incidence of adverse events in general and by seriousness, severity and association to the device. Treatment tolerability The percent of subjects who fail to complete the study because of adverse events
Datasets	 Intent to treat analysis set (ITT) The ITT analysis set includes all participants undergoing the treatment phase. Modified intent to treat analysis set (mITT) The mITT analysis set includes all participants undergoing the treatment phase who treat a test treatment within 60 minutes of attack onset.
Data Analysis	The ITT analysis set will be used for the primary endpoints of safety and tolerability assessments. Safety assessments will include spontaneously reported adverse events. The mITT analysis set will be used for the efficacy assessments.

Revision #: 1.0

Page: 9 of 20

2. Background

REN is a novel treatment option which has successfully been shown to reduce migraine headaches in the adult population (Yarnitsky et al, 2020). There is now data to support its use in pediatrics and the device was recently FDA approved for use in pediatric migraine patients ages 12 years and older (Hershey et al, 2021). New daily persistent headache is a constant, unremitting headache disorder with clinical symptoms of migraine and/or tension-type headache and is seen in as many as 14% of pediatric and adolescents patients (Strong et al, 2021). Pediatric patients with a diagnosis of new daily persistent headache are typically resistant to standard pharmacologic treatments and often experience systemic side effects related to medications; thus, REN offers the potential for an exciting new treatment option for patients with refractory headache disorders.

3. Identification and description of the device information

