During the training, participants will also be informed on the key elements which are critical for the successful conduct of the study:

Revision #: 1.0 Page: 13 of 20

- Treatments of headache with Nerivio[™] should be performed within 60 minutes of awakening with a headache or upon increasing headache severity and always within one hour of symptoms onset. Treatments of mild headaches are accepted.
- Avoid taking rescue medications within two hours post-treatment (2 hours from start of treatment), if possible.

Revision #: 1.0

Page: 14 of 20

• The treatment should be performed for 45 minutes.

In addition, participants will complete study questionnaires, as required.

Phase 2 – Treatment phase: Participants will be instructed to use the device within 60 minutes of awakening with a headache or upon increasing headache severity during a period of 4 week. Participants will be instructed to use the device with the intensity level identified during the device training visit (with a range of ±5 units) and make sure the stimulation is perceptible but not painful. Participants will be instructed to avoid taking rescue medications within 2 hours post-treatment. If medications are used, participants will be instructed to record in the app when and which medication was taken. The participants will use the app to record pain intensity levels (none, mild, moderate, or severe) at baseline and 2 hours post-treatment, and to record the presence/absence of associated symptoms (nausea, photophobia, phonophobia) at baseline and 2 hours post-treatment.

Participants who do not achieve satisfactory relief at 2 hours post-treatment may treat again with the Nerivio[™] device or may treat with usual care at that time or any time thereafter if the headache does not resolve.

Third (final) visit – End of study: Participants will return to the clinic following the end of the 4-week treatment phase, at which time they will return the device and complete the required questionnaires

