5.3.4. Safety endpoints

1. The safety of Nerivio

The incidence of adverse events in general and by seriousness, severity and association to the device.

2. Treatment tolerability

The percent of subjects who fail to complete the study because of adverse events.

6. Statistical Considerations

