6.4.3. Safety analysis

Safety and tolerability will be assessed by review of all safety parameters, including adverse events. Serious adverse events, device-related SAEs, adverse events (by type and overall), device-related AE, adverse device reactions and device malfunction rates will be documented. Treatment tolerability, the number and percent of subjects who fail to complete the study and the number and percent of subjects who fail to complete the study because of adverse events will be presented. Time to withdrawal will also be assessed and presented by Kaplan-Meier curves.

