7.2. Records and data retention

A copy of all records (e.g., informed consent documents, source data, safety reports, study device dispensing records, etc.) which support case report forms for this study, will be retained in the files of the responsible investigator for a minimum of five (5) years.

The Food and Drug Administration (FDA) and/or the local state health authorities may request access to all study records, including source documents, for inspection. The investigator and site staff agree to cooperate with these audits.

8. Device accountability

The devices will be provided by Theranica Bioelectronics (Netanya, ISRAEL). The device serial number will be documented when provided to the participant.

The devices will only be used in the clinical investigation and according to the study protocol.

The investigator will be responsible for providing device training to the participants according to the instructions for use. If the participant damages or loses the device, we can replace up to one device per participant, if needed. We will not request any compensation for that or hold any claims for that.

9. Informed consent processrescue

Informed consent and assent must be obtained from the parent/caregiver and participant, respectively, before any protocol-related activities are performed. Participants must be provided with a signed copy of the consent and assent forms.

10. Adverse events

Adverse event (AE) is defined as any unfavorable and unintended medical change, temporally associated with the use of the Nerivio, whether or not considered related to the use of the product. Any worsening (i.e., any clinically significant adverse change in frequency and/or intensity) of a preexisting condition which is temporally associated with the use of the device, is also an adverse experience. An adverse device effect (ADE) is an adverse event related to the use of the Nerivio device. In this study the ADE refers to side effect and complications.

A serious adverse event (SAE) is defined as an adverse event that leads to

Revision #: 1.0 Page: 19 of 20

- a) death,
- b) serious deterioration in the health of the subject, that either resulted in
 - 1) a life-threatening illness or injury, or
 - 2) a permanent impairment of a body structure or a body function, or
 - 3) in-patient or prolonged hospitalization, or
 - 4) medical or surgical intervention to prevent life-threatening illness or injury or permanent impairment to body structure or body function

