10.2. Reporting of AEs and SAEs

All adverse events will be recorded in appropriate adverse events case report form. The adverse events will be used for the safety assessment.

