10.3. Anticipated device-related AEs

Possible adverse events associated with remote electrical neuromodulation include, but are not limited to, the following:

- Numbness of the hand/arm
- Itching
- Muscle spasms
- Redness
- Warmth sensation
- Tingling
- Pain in the arm

All anticipated devoice-related AEs, if present, are temporary and should disappear shortly after the treatment.

The following migraine symptoms are foreseeable and will not be considered as device related: headache, nausea, light sensitivity, sensitivity to noise, allodynia, abdominal pain, loss of appetite, cold or heat sensation, paleness, fatigue, dizziness, anxious mood, fever (rare), blurred vision, vision symptoms such as bright flashing dots or lights, blind spots, wavy or jagged lines (aura).

11. Patient confidentiality & data protection

The privacy of the participants and the confidentiality of all personal data will be maintained in reports and publications and will not be otherwise published in any way. The privacy will be maintained according to prevailing national data protection, privacy and secrecy laws. Each patient will be identified by a unique patient identification number.

12. Guidelines and applicable documents

- EN ISO 14155; (2011): Clinical investigation of medical devices for human patients
- EN ISO 14971; (2012): Medical devices Application of risk management to medical devices
- International Conference of Harmonization Good Clinical Practice guidelines
- FDA Guidance for Industry: Computerized Systems Used in Clinical Investigations

Revision #: 1.0

Page: 20 of 20

13. Reference

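### Spontaneous reporting is the only adverse-event method the plan names, and no rule links app-recorded worsening to adverse-event review, so AE incidence is likely to be under-ascertained.

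*Combined protocol and SAP*

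**What the plan says.** - **How AEs are found.** The Synopsis (Data Analysis) says "Safety assessments will include spontaneously reported adverse events". Section 6.4.3 says "Safety and tolerability will be assessed by review of all safety parameters, including adverse events", and section 10.2 says "All adverse events will be recorded in appropriate adverse events case report form". None of these states who asks about AEs, when, or in what words.
- **Visits and app entries.** Section 5.2 describes up to three visits. The device is self-administered for 4 weeks between the second and third. At the third, participants come back to the clinic, "at which time they will return the device and complete the required questionnaires"; those questionnaires are not itemised. The Phase 2 app entries are pain grade, three associated symptoms and any medication taken.
- **Expected reactions.** Section 10.3 lists numbness, itching, muscle spasms, redness, warmth, tingling and arm pain, which, "if present, are temporary and should disappear shortly after the treatment".
- **Worsening as an AE.** Section 10 includes as an adverse experience "Any worsening (i.e., any clinically significant adverse change in frequency and/or intensity) of a preexisting condition" when it is temporally associated with device use. Section 10.3 classes headache, nausea, and light and noise sensitivity as not device related.
- **Endpoint.** The first safety endpoint in 5.3.4 is: "The incidence of adverse events in general and by seriousness, severity and association to the device".

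**The concern.** The expected reactions are brief and occur at home, and the next listed visit is at the end of the 4 weeks. By the protocol's own account most will have resolved by then. Whether they reach the case report form depends on an adolescent remembering them and raising them unprompted.

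The second gap is internal to the plan. Section 10 brings clinically significant worsening within the AE definition. The app records pain grade, nausea, photophobia and phonophobia before treatment and at 2 hours, so candidate worsening will already be in the database. No section says that anyone looks at these entries for AEs. The 2-hour endpoints in 5.3 and 6.4.4 count relief, disappearance of a symptom, or improvement in function. The training treatment, which is the first exposure, is left out of the efficacy analyses altogether.

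A favourable safety profile is half of the hypothesis in 4.2. With a single arm there is no comparator subject to the same under-reporting, so a low AE rate could reflect few events or few reports, and the results would not show which.

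**Working it through.** **Is there a figure to reproduce?** No. The documents give no expected AE rate, no capture fraction and no precision target, and the sample size of 100 in 6.2 has no derivation. What follows is illustration under stated assumptions.

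**Step 1. Where could an AE enter the record?**

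| Source | What the plan provides | Covers brief local reactions? |
|---|---|---|
| Spontaneous report (Synopsis) | Named | Only if volunteered |
| AE case report form (10.2) | Place to record, no method of asking | No method stated |
| Final visit (5.2) | Device return, questionnaires not itemised | No AE enquiry listed |
| App in Phase 2 (5.2) | Pain, three symptoms, medication | No AE prompt listed |
| C-SSRS (Synopsis, 5.2) | Solicited at in-clinic visits | No, suicidality only |
| HIT-6 (Synopsis, exploratory) | Described as touching adverse reactions | Not routed to the AE form; not named in 5.3.3 |

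**Step 2. Effect of incomplete capture.** Let p be the true per-participant incidence and c the fraction of affected participants who are captured. The expected observed proportion is p × c, so under-capture lowers the estimate in proportion. Take p = 20% (assumed) and n = 100 (the planned maximum), with exact (Clopper-Pearson) 95% intervals:

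| c (assumed) | p × c × 100 | 95% CI | Contains 20%? |
|---|---|---|---|
| 1.00 | 20 | 12.7 to 29.2% | Yes |
| 0.75 | 15 | 8.6 to 23.5% | Yes |
| 0.70 | 14 | 7.9 to 22.4% | Yes |
| 0.50 | 10 | 4.9 to 17.6% | No |
| 0.30 | 6 | 2.2 to 12.6% | No |

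**Step 3. Coverage.** With X ~ Binomial(100, p × c), the chance that the nominal 95% interval contains the true p is:

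| p (assumed) | c = 1 | c = 0.75 | c = 0.5 |
|---|---|---|---|
| 10% | 95.6% | 87.6% | 56.4% |
| 20% | 96.7% | 83.6% | 29.7% |

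The interval reflects sampling error only and does not correct for missed reports. Likewise, no events in 100 gives an upper 95% limit of 3.6%, which is valid only if capture is complete.

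**Step 4. Sensitivity to n.** The plan says up to 100, and the safety set is those who enter the treatment phase after the run-in. If 60 are treated (assumed), p = 20% and c = 0.5 give 60 × 0.20 × 0.5 = 6, and 6/60 has a 95% CI of 3.8 to 20.5%, which includes 20%. The proportional bias is the same; the wider interval hides it.

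**Step 5. What a worsening table might show.** If each session independently carries a chance q of worsening, the share of participants with at least one worsened session over m sessions is 1 − (1 − q)^m:

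| q (assumed) | m = 8 | m = 28 |
|---|---|---|
| 1% | 7.7% | 24.5% |
| 2% | 14.9% | 43.2% |
| 5% | 33.7% | 76.2% |

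The participant-level percentage depends heavily on how often the device is used, so a per-session percentage is needed beside it.

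**The case against.** The strongest reply is that the plan says safety assessments will include spontaneous reports, not that they consist of them. Section 6.4.3 also covers device malfunctions, withdrawals and time to withdrawal, and the C-SSRS is solicited. This stands as far as it goes: a reader might infer that spontaneous reports are the sole safety information, and the documents do not support that. But none of the other sources asks about local reactions, so the gap in ascertainment remains.

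Other stronger readings also fail:

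- **That there is no contact between visits 2 and 3.** The documents list none but do not exclude it, and device replacement (section 8) makes some contact possible.
- **That app-recorded worsening is excluded from safety.** The documents are silent on its use; they do not rule it out.
- **That no analysis can reflect worsening.** Average headache intensity at 1 month and PedsMIDAS are changes in averages, and worsening would enter them. What is missing is a count of worsened participants or sessions at 2 hours.
- **That every rise in pain grade is an AE.** Section 10 requires a clinically significant change. Participants may treat as severity is increasing, so a higher grade at 2 hours may be the natural course of the attack, and one arm cannot separate the two.

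It is also fair to say that 10.3 already treats headache, nausea, and light and noise sensitivity as not device related. That rule concerns attribution and does not remove AE status. Its consequence is that reviewing app data would mainly affect overall AE incidence, not the device-related rate.

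Finally, one question at the final visit cannot fully cure recall loss over 4 weeks, and a checklist that includes tingling and warmth may pick up the intended sensation, since stimulation is meant to be perceptible. Both objections stand and are met in the fix.

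**Conclusion.** The point holds in this form: spontaneous reporting is the only AE ascertainment method named, no scheduled AE enquiry is listed for the home phase or the final visit, and no rule connects app-recorded worsening to the section 10 definition. Under-ascertainment of the first safety endpoint is likely, and its direction is downward.

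Its size cannot be derived from the documents. The 20% incidence and the capture fractions of 30 to 75% are assumptions. At n = 100 the interval excludes an assumed true 20% when capture is 30% or 50%, but not at 70% or 75%; with 60 treated it does not exclude 20% even at 50%. A reader might conclude that AE incidence will certainly be too low; the documents support likely, not certain.

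This is worth changing before the study starts because it bears on a stated endpoint and the remedy is small.

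**What to change.** **1. Scripted AE enquiry.** At the third visit and at any early withdrawal, ask one open AE question, then go through the 10.3 list. Report volunteered and elicited events separately. Record separately any sensation felt only during stimulation, such as tingling or warmth. State that recall over 4 weeks remains a limitation.

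**2. Descriptive worsening table from existing app data, including the training treatment.**
- Give the percent of participants with a higher pain grade at 2 hours than at treatment start, or with new nausea, photophobia or phonophobia, with exact 95% confidence intervals.
- Give the percent of sessions as well, with an interval that allows for repeated sessions within participant.
- Label it a descriptive safety table. Note that pain already severe at the start cannot rise on this scale, and that natural fluctuation cannot be separated in a single arm.
- Have the investigator review the cases against the clinically significant criterion in section 10, and reconcile that review with the attribution rule in 10.3.

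**Cost.** A short script at an existing visit, one extra table and the investigator's time for case review; no new data collection in the app. The reported overall AE rate may rise, and prompted reports may include minor expected sensations, which is why the volunteered and elicited counts are kept apart.
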